13.6. Institutional Review Board/Independent Ethics Committee Review and Approval

Before the start of the study, the study protocol, ICF, and any other appropriate documents will be submitted to the IRB/EC with a cover letter or a form listing the documents submitted, their dates of issue, and the site (or region or area of jurisdiction, as applicable) for which approval is sought. If applicable, the documents will also be submitted to the authorities in accordance with local legal requirements.

The IP can only be supplied to an Investigator by Celgene or its authorized representative after documentation on all ethical and legal requirements for starting the study has been received by Celgene or its authorized representative. This documentation must also include a list of the members of the IRB/EC and their occupation and qualifications. If the IRB/EC will not disclose the names, occupations and qualifications of the committee members, it should be asked to issue a statement confirming that the composition of the committee is in accordance with GCP. For example, the IRB General Assurance Number may be accepted as a substitute for this list. Formal approval by the IRB/EC should mention the protocol title, number, amendment number (if applicable), study site (or region or area of jurisdiction, as applicable), and any other documents reviewed. It must mention the date on which the decision was made and must be officially signed by a committee member. Before the first subject is enrolled in the study, all ethical and legal requirements must be met.

The IRB/EC and, if applicable, the authorities, must be informed of all subsequent protocol amendments in accordance with local legal requirements. Amendments must be evaluated to determine whether formal approval must be sought and whether the ICF should also be revised.

The Investigator must keep a record of all communication with the IRB/EC and, if applicable, between a Coordinating Investigator and the IRB/EC. This statement also applies to any communication between the Investigator (or Coordinating Investigator, if applicable) and regulatory authorities.

Any advertisements used to recruit subjects for the study must be reviewed by Celgene and the IRB/EC prior to use.

13.7. Ongoing Information for Institutional Review Board/ Ethics Committee

If required by legislation or the IRB/EC, the Investigator must submit to the IRB/EC:

- Information on serious or unexpected AEs as soon as possible
- Periodic reports on the progress of the study
- Deviations from the protocol or anything that may involve added risk to subjects

13.8. Termination of the Study

Celgene reserves the right to terminate this study prematurely at any time for reasonable medical or administrative reasons. Any premature discontinuation will be appropriately documented according to local requirements (eg, IRB/EC, regulatory authorities, etc).

In the case where there are subjects still being administered the investigational product, and it is the opinion of the Investigator(s) that these subjects continue to receive benefit from treatment, the Sponsor may choose to initiate an open-label, extension study under a separate protocol to allow these subjects continued access to pomalidomide following their participation in this study (CC-4047-BRN-001).

In addition, the Investigator or Celgene has the right to discontinue a single site at any time during the study for medical or administrative reasons such as:

- Unsatisfactory enrollment

- GCP noncompliance
- Inaccurate or incomplete data collection
- Falsification of records
- Failure to adhere to the study protocol

CELGENE PROPRIETARY INFORMATION

14. DATA HANDLING AND RECORDKEEPING

14.1. Data/Documents

The Investigator must ensure that the records and documents pertaining to the conduct of the study and the distribution of the IP are complete, accurate, filed and retained. Examples of source documents include: hospital records; clinic and office charts; laboratory notes; memoranda; subject's diaries or evaluation checklists; dispensing records; recorded data from automated instruments; copies or transcriptions certified after verification as being accurate copies; microfiche; x-ray film and reports; and records kept at the pharmacy, and the laboratories, as well as copies of eCRFs or CD-ROM.

14.2. Data Management

Data will be collected via eCRF and entered into the clinical database per Celgene standard operating procedures (SOPs). This data will be electronically verified through use of programmed edit checks specified by the clinical team. Discrepancies in the data will be brought to the attention of the clinical team, and investigational site personnel, if necessary. Resolutions to these issues will be reflected in the database. An audit trail within the system will track all changes made to the data.

14.3. Record Retention

Essential documents must be retained by the Investigator according to the period of time outlined in the clinical trial agreement. The Investigator must retain these documents for the time period described above or according to local laws or requirements, whichever is longer. Essential documents include, but are not limited to, the following:

- Signed ICFs/IAFs for all subjects
- Subject identification code list, screening log (if applicable), and enrollment log
- Record of all communications between the Investigator and the IRB/EC
- Composition of the IRB/EC
- Record of all communications between the Investigator, Celgene, and their authorized representative(s)
- List of Sub-investigators and other appropriately qualified persons to whom the Investigator has delegated significant study-related duties, together with their roles in the study, curriculum vitae, and their signatures
- Copies of eCRFs and of documentation of corrections for all subjects
- IP accountability records
- Record of any body fluids or tissue samples retained
- All other source documents (subject records, hospital records, laboratory records, etc.)

- All other documents as listed in Section 8 of the ICH consolidated guideline on GCP (Essential Documents for the Conduct of a Clinical Trial)

The Investigator must notify Celgene if he/she wishes to assign the essential documents to someone else, remove them to another location or is unable to retain them for a specified period. The Investigator must obtain approval in writing from Celgene prior to destruction of any records. If the Investigator is unable to meet this obligation, the Investigator must ask Celgene for permission to make alternative arrangements. Details of these arrangements should be documented.

All study documents should be made available if required by relevant health authorities. The Investigator or institution should take measures to prevent accidental or premature destruction of these documents.

15. QUALITY CONTROL AND QUALITY ASSURANCE

All aspects of the study will be carefully monitored by Celgene or its authorized representative for compliance with applicable government regulations with respect to current GCP and SOPs.

15.1. Study Monitoring and Source Data Verification

Celgene ensures that appropriate monitoring procedures are performed before, during and after the study. All aspects of the study are reviewed with the Investigator and the staff at a study initiation visit and/or at an Investigators' Meeting. Prior to enrolling subjects into the study, a Celgene representative will review the protocol, eCRFs, procedures for obtaining informed consent/assent, record keeping, and reporting of AEs/SAEs with the Investigator. Monitoring will include on-site visits with the Investigator and his/her staff as well as any appropriate communications by mail, email, facsimile, or telephone. During monitoring visits, the facilities, IP storage area, eCRFs, subject's source documents, and all other study documentation will be inspected/reviewed by the Celgene representative in accordance with the Study Monitoring Plan.

Accuracy will be checked by performing source data verification that is a direct comparison of the entries made onto the eCRFs against the appropriate source documentation. Any resulting discrepancies will be reviewed with the Investigator and/or his/her staff. Any necessary corrections will be made directly to the eCRFs or via queries by the Investigator and/or his/her staff. Monitoring procedures require that informed consents/assents, adherence to inclusion/exclusion criteria and documentation of SAEs and their proper recording be verified. Additional monitoring activities may be outlined in a study-specific monitoring plan.

15.2. Audits and Inspections

In addition to the routine monitoring procedures, a Good Clinical Practice Quality Assurance unit exists within Celgene. Representatives of this unit will conduct audits of clinical research activities in accordance with Celgene SOPs to evaluate compliance with Good Clinical Practice guidelines and regulations.

The Investigator is required to permit direct access to the facilities where the study took place, source documents, eCRFs and applicable supporting records of study subject participation for audits and inspections by IRB/ECs, regulatory authorities (eg, FDA, European Medicines Agency [EMA], Health Canada) and company authorized representatives. The Investigator should make every effort to be available for the audits and/or inspections. If the Investigator is contacted by any regulatory authority regarding an inspection, he/she should contact Celgene immediately.

16. PUBLICATIONS

As described in Section 13.2, all protocol- and amendment-related information, with the exception of the information provided by Celgene on public registry websites, is considered Celgene confidential information and is not to be used in any publications. Celgene protocol-related information proposed for use in a publication must be submitted to Celgene for review and approval, and should not be utilized in a publication without express written approval from Celgene, or as described in the Clinical Trial Agreement.

Celgene will ensure Celgene-sponsored studies are considered for publication in the scientific literature in a peer-reviewed journal, irrespective of the results. At a minimum, this applies to results from all Phase 3 clinical studies, and any other study results of significant medical importance. This also includes results relating to investigational medicines whose development programs have been discontinued.

Study results may also be presented at one or more medical congresses, and may be used for scientific exchange and teaching purposes. Additionally, this study and its results may be submitted for inclusion in all appropriate health authority study registries, as well as publication on health authority study registry websites, as required by local health authority regulations.

Eligibility for external authorship, as well as selection of first authorship, will be based on several considerations, including, but not limited to, contribution to protocol development, study recruitment, data quality, participation in data analysis, participation in study SC (when applicable) and contribution to abstract, presentation and/or publication development.

18. APPENDICES

Appendix A: Table of Abbreviations

Table 9: Abbreviations and Specialist Terms

Abbreviation or Specialist Term	Explanation
AE	Adverse event
AED	Anti-epileptic drugs
ALT	Alanine aminotransferase (SGPT)
ANC	Absolute neutrophil count
ATRT	Atypical teratoid rhabdoid tumor
AUC	Area under the curve
β-FGF	Basic fibroblast growth factor
β-Hcg	β-subunit of human chorionic gonadotropin
BSA	Body surface area
CDK	Cyclin-dependent kinase
CI	Confidence interval
CL/F	Clearance
C _{max}	Maximum plasma concentration of drug
CNS	Central nervous system
COG	Children oncology group
CR	Complete response
CRBN	Cereblon protein
CRO	Contract research organization
CSF	Cerebrospinal fluid
CTCAE	Common terminology criteria for adverse events
CUL4	Cullin 4
CYP	Cytochrome P450
DDB1	DNA Damage-binding protein 1
DIPG	Diffuse intrinsic pontine glioma
DLT	Dose-limiting toxicity
DMC	Data Monitoring Committee
DoR	Duration of response
EC	Ethics Committee

Table 9: Abbreviations and Specialist Terms (Continued)

Abbreviation or Specialist Term	Explanation
eCRF	Electronic case report form
EEA	European Economic Area
EMA	European Medicines Agency
EOT	End of treatment
EU	European Union
FCBP	Females of childbearing potential
FCCBP	Female children of childbearing potential
FDA	Food and Drug Administration
FLAIR	Fluid-attenuated inversion recovery
GBM	Glioblastoma multiforme
GCP	Good Clinical Practice
G-CSF	Granulocyte colony-stimulating factor
GFR	Glomerular filtration rate
GTR	Gross total resection
GVHD	Graft versus host disease
HDPE	High density polyethylene
IAF	Informed assent form
ICF	Informed consent form
ICH	International Council on Harmonisation
ID	Identification number
IIT	Investigator initiated trial
IL	Interleukin
IND	Investigational new drug
IFN- γ	Interferon-gamma
IP	Investigational product
IR	Incomplete response
IRF4	Interferon regulatory factor 4
IRB	Institutional review board
IRT	Interactive Response Technology
ITT	Intent to treat

Table 9: Abbreviations and Specialist Terms (Continued)

Abbreviation or Specialist Term	Explanation
MAA	Marketing authorization application
MDS	Myelodysplastic syndromes
MedDRA	Medical Dictionary for Regulatory Activities
MF	Myelofibrosis
MM	Multiple myeloma
MRI	Magnetic resonance imaging
MTD	Maximum tolerated dose
NCI	National cancer institute
NCS	Not clinically significant
NF1	Neurofibromatosis type 1
NHL	non-Hodgkin's lymphoma
NK	Natural killer
NLME	Nonlinear mixed-effect
O ₂	Oxygen
OAT	Organic anion transporter
OCT	Organic cation transporter
OR	Objective response
ORR	Objective response rate
ORSDR	Objective response and long-term stable disease rate
OS	Overall survival
PA	Pilocytic astrocytoma
PBTC	Pediatric Brain Tumor Consortium
PD	Progressive disease
PFS	Progression-free survival
PR	Partial response
PK	Pharmacokinetics
PNET	Primitive neuroectodermal tumor
RBC	Red blood cell count
RP2D	Recommended phase 2 dose

Table 9: Abbreviations and Specialist Terms (Continued)

Abbreviation or Specialist Term	Explanation
SAE	Serious adverse event
SC	Steering committee
SCT	Stem cell transplant
SD	Stable disease
SOP	Standard operating procedure
SPM	Second primary malignancy
SUSAR	Suspected unexpected serious adverse reaction
$t_{1/2}$	Half-life
TBI	Total body irradiation
TEAE	Treatment emergent adverse event
TEN	Toxic epidermal necrolysis
TGF- α	Transforming growth factor alpha
Th1	T helper cell type 1
T_{max}	Time to maximum plasma concentration
TNF- α	Tumor necrosis factor-alpha
tPA	Tissue plasminogen activator
ULN	Upper limit of normal
Vd/F	Volume of distribution
VEGF	Vascular endothelial growth factor
WBC	White blood cell
WHO	World Health Organization

Appendix B: Tumor Response Categories for Target and Non-target Lesions

Target Lesions

For the purpose of this study, response criteria for target lesions are defined as follows:

- **Complete Response (CR):**
 - Complete disappearance on MRI of all measurable lesions.
- **Partial Response (PR):**
 - A reduction of $\geq 50\%$ in tumor size by bi-dimensional measurement (taking as reference the baseline measurements) quantified by the sum of the products of the perpendicular diameters of measurable lesions.
- **Stable Disease (SD):**
 - A decrease of $< 50\%$ or an increase of $< 25\%$ in the sum of the products of the perpendicular diameters of measurable lesions and no evidence of new lesions. Response does not meet the criteria for CR, PR or PD.
- **Progressive Disease (PD):**
 - $\geq 25\%$ increase in the bi-dimensional measurement as quantified by the sum of the products of the largest diameters of the measurable lesions taking as a reference the smallest disease measurement recorded since the start of protocol therapy (nadir).

Non-target Lesions

For the purpose of this study, response criteria for non-target lesions are defined as follows:

- **Complete Response (CR):**
 - Disappearance of all non-target lesions.
 - If spine MRI and/or lumbar CSF cytology were previously positive, it must be negative at time of assessment.
- **Incomplete Response/Stable Disease (IR/SD):**
 - The persistence of non-target lesions, stable (no progression) or decrease in size.
 - If spine MRI and/or lumbar CSF cytology were previously positive at baseline and remains positive with no other evidence of PD.
- **Progressive Disease (PD):**
 - The appearance of one or more new lesions and/or unequivocal progression of existing non-target lesions.
 - If spine MRI and/or lumbar CSF cytology were previously negative and became positive.

Appendix C: Overall Response Assessment

The overall response assessment takes into account response in both target (Appendix B) and non-target lesions (Appendix B), the appearance of new lesions, current corticosteroid use (compared to baseline) and neurologic symptoms/examination (clinical status) according to the criteria below (Table 10). Subjects who do not meet the criteria for an objective response or disease progression by the end of Cycle 6 (end of Cycle 3 for DIPG subjects) will be considered as having long-term SD.

Table 10: Overall Response Assessment

Criterion	Overall Response				
	Complete Response	Partial Response		Stable Disease	Progression
Target lesions	CR	PR	CR	SD	PD
Non-Target lesions	CR	CR or IR/SD	IR/SD	CR or IR/SD	PD
New Lesion	None	None	None	None	Present
Corticosteroids	None ^a	Stable or Decreasing ^b	Stable or Decreasing ^b	Stable or Decreasing ^b	Not Applicable ^c
Clinical Status (neurologic examination)	Stable or Improved	Stable or Improved	Stable or Improved	Stable or Improved	Decreasing ^d
Requirement for Response	All	All	All	All	Any ^e

CR = complete response; IR = incomplete response; PR = partial response; SD = stable disease; PD = progressive disease.

^a Only physiologic replacement doses allowed, defined as no more than 0.75 mg/m²/day of dexamethasone or equivalent.

^b Not greater dose than compared with baseline.

^c An increase in corticosteroid dose alone will not cause a determination of progression in the absence of clinical deterioration or radiographically documented lesion growth.

^d Neurologic abnormalities or worsening neurologic status not explained by causes unrelated to tumor progression (eg, anticonvulsant or corticosteroid toxicity, wean, electrolyte disturbances, sepsis, hyperglycemia, etc.) or changes in corticosteroid dose.

^e Progression occurs when any of these criteria are met present.

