6.4.1.7. Overall Response Assessment

The overall response assessment takes into account response in both target and non-target lesions, the appearance of new lesions, current corticosteroid use (compared to screening/baseline) and neurologic symptoms/examination (clinical status) according to the criteria described in [Appendix C](#).

Subjects who do not meet the criteria for an objective response or disease progression by the end of Cycle 6 (end of Cycle 3 for DIPG subjects) will be considered as having long-term SD.

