6.1. Analysis of Primary Efficacy Endpoint

6.1.1. Objective Response and Long-term Stable Disease Rate

The ORSDR is defined as the percentage of subjects that achieve either a CR, PR or SD maintained for ≥ 6 cycles (≥ 3 cycles for the DIPG tumor type/disease indication) as their best response, divided by the total number of subjects available for the analysis within the given population, eg, subjects contained within the Response Population (primary analysis), the ITT Population, and the Safety Population as outlined within Section 5 of this SAP. The ITT Population will not be used should all enrolled subjects have received at least one dose of study drug. Non-responder subjects are considered subjects with a PD as best response, subjects not having a postbaseline assessment or subjects having not evaluable recorded on their postbaseline assessment(s). The corresponding 2-sided, 95% Clopper-Pearson confidence interval (CI) will also be provided.

Calculation of SD duration starts at the time of first dose of pomalidomide and continues until the date of the first observation of PD is recorded or death due to any cause, regardless of whether the subject achieves a CR and/or PR within that period, or until the date of the last disease assessment if no PD or death is recorded; if the difference is ≥ 6 cycles (≥ 3 cycles for the DIPG tumor type/disease indication), ie, the subject has not had a documented PD before Cycle 7, Day 1 (Cycle 4, Day 1 for the DIPG tumor type/disease indication) and has completed 6 cycles of pomalidomide (3 cycles for the DIPG tumor type/disease indication), then the SD will be considered as being maintained for ≥ 6 cycles (≥ 3 cycles for the DIPG tumor type/disease indication).

For identification of PD for this SD duration calculation, PD is classified as a PD as observed during a response assessment (both during the Treatment Period and the Follow-up Period if applicable); the first time this occurrence is observed is selected as the PD date.

Disease assessments recorded on or after start of a new anticancer therapy will not be considered, nor will disease assessments reported after a PD has been observed.

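### Table 10 has no overall response category for a tumor that disappears completely on an unchanged therapeutic steroid dose, so ORR and duration of response can miss it

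*Protocol*

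**What the plan says.** Protocol Appendix C, Table 10, builds the overall response from target lesions, non-target lesions, new lesions, corticosteroids and clinical status. Read across the columns CR, PR, PR, SD and progression, the two lesion rows are "Target lesions CR PR CR SD PD" and "Non-Target lesions CR CR or IR/SD IR/SD CR or IR/SD PD". The closing row, "Requirement for Response All All All All Any", means that CR, PR and SD need every criterion in their column, while one criterion is enough for progression.

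The steroid row differs by column. For CR, footnote a says "Only physiologic replacement doses allowed, defined as no more than" 0.75 mg/m²/day of dexamethasone or equivalent. For both PR columns and for SD, footnote b says "Not greater dose than compared with baseline". Section 6.4.1.6 gives the same meaning to a stable or decreasing dose. It adds that physiologic replacement doses are taken into account in the overall assessment, but does not say how.

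Section 6.4.1.7, repeated in Appendix C, supplies a default: "Subjects who do not meet the criteria for an objective response or disease progression by the end of Cycle 6" (Cycle 3 for DIPG) are classed as long-term SD.

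In the SAP, ORR counts CR or PR as best response, and best response is one of CR, PR, SD, PD or not evaluable (6.2.1). DoR starts at the initial CR or PR (6.2.3). For the primary endpoint, SD counts as long-term only if 6 cycles (3 for DIPG) were completed without documented PD, and the non-responders include "subjects having not evaluable recorded on their postbaseline assessment(s" (6.1.1).

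**The concern.** A response scale should not score a deeper response below a shallower one when everything else is equal. Table 10 does so in one cell. If every lesion disappears while the child is still on the baseline therapeutic steroid dose, the CR column is closed by footnote a and no PR column is open.

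The case can arise. Inclusion criterion 7 (Section 4.2) admits children on steroids, Section 8.1.2 permits doses above replacement and calls them therapeutic, and Section 6.4.1.1 says that most of these tumors are a single lesion. At stake are the secondary response endpoints (ORR, best overall response and DoR) and, in narrower circumstances, the primary objective response and long-term stable disease rate (ORSDR).

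**Working it through.** **1. The cell, column by column.** Take target CR, non-target CR, no new lesion, stable or improved clinical status, and a steroid dose above 0.75 mg/m²/day but not above baseline.

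- CR fails on steroids (footnote a).
- The first PR column fails because it needs target PR.
- The second PR column fails because it needs non-target IR/SD.
- SD fails because it needs target SD, which Appendix B limits to a decrease below 50%.
- Progression fails because no progression criterion is met.

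**2. The same child and the same steroid dose, side by side.**

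| Target | Non-target | Overall response |
|---|---|---|
| PR | CR or IR/SD | PR |
| CR | IR/SD | PR |
| CR | CR | none |

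**3. Is it the only such cell?** The grid is target (4 states) × non-target (3) × new lesion (2) × steroid (3: none or physiologic; therapeutic but not above baseline; above baseline) × clinical status (2) = 144 combinations. Applying all criteria for CR, PR and SD and any criterion for progression leaves 7 without a category. Six have a dose above baseline. The seventh is the cell above, the only gap at or below the baseline dose. The grid puts no steroid and replacement dosing in one state, so it does not test whether newly started replacement counts as an increase. That question rests on the text of footnotes a and b and Section 6.4.1.6.

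**4. The single-lesion child.** Table 10 has no entry for absent non-target disease. Such a child can reach overall CR only if absence is read as non-target CR. That reading puts the same child, on a therapeutic dose, in the empty cell.

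**5. Effect on each endpoint.**

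- *ORR, best response, DoR.* If an earlier scan was rated PR, all three keep the response. If the steroid is later weaned to replacement or below with the disappearance sustained, ORR and best response recover as CR, but DoR starts late. If neither happens, ORR and best response miss the response and DoR omits the child. Outside DIPG, scheduled brain MRI falls on Day 1 of Cycles 3, 5 and 7; in DIPG the first is Cycle 4 Day 1 (Section 6.4.1), so an earlier PR scan is less likely there.
- *ORSDR.* The default classes the child as long-term SD, which is a success. The success is lost only if the child stops before completing 6 (3) cycles without ever being rated PR or CR, or if the scan is recorded as not evaluable.

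**6. Size.** One child is 1/20 = 5 points of ORR in a full stratum and 1/9 = 11 points in a stratum closed after Stage 1.

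**7. The plan's own design figure**, for context. The probability of a positive stratum is the sum over x = 2 to 9 of P(X1 = x) × P(X2 ≥ max(0, 5 − x)), with X1 ~ Bin(9, p) and X2 ~ Bin(11, p). At p = 0.10 it is 0.0349 and at p = 0.40 it is 0.9018, so the stated 5% and 90% reproduce. The cut-offs of 2/9 and 5/20 apply to ORSDR, not to ORR.

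**The case against.** The best counter-reading is that a 100% reduction is also a reduction of at least 50%. Appendix B puts no upper limit on target PR and, unlike SD, does not exclude CR, so the child would enter the first PR column. Table 10 itself argues against this. The first PR column already accepts non-target IR/SD with otherwise identical rows, so if target CR counted as target PR, the separate column for target CR with IR/SD would be redundant. The table treats the two as distinct states. That reading also ends at PR, which is what the added column would say.

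Three other objections stand and limit the point:

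- An earlier PR scan or a later wean preserves ORR, and Section 8.1.2 asks for the lowest steroid dose consistent with good management.
- Few responses may occur at all. The pediatric response data that the protocol gives are for lenalidomide, a related drug in different tumor mixes: no objective responses among 49 children in one study, and two partial responses among 44 evaluable in the other (Section 1.3.1).
- The independent review charter (Section 6.4.1.8) is not among the documents and may already settle the case.

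Two stronger readings are tempting. A reader might infer that one such child alone decides 1/9 versus 2/9 or 4/20 versus 5/20. The documents do not support that as the usual result, because those cut-offs count long-term SD as success and the default supplies it. No text says that an uncategorized scan is recorded as not evaluable. A reader might also infer a second clear error, in that footnote a spares replacement dosing for CR while footnote b does not for PR or SD. Section 6.4.1.6 does bring replacement doses into the overall assessment, so this is an ambiguity to resolve.

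**Conclusion.** The point holds for the secondary response endpoints. Followed as written, Table 10 and the default turn a complete disappearance on an unchanged therapeutic dose into long-term SD, while a lesser response on the same dose is PR. This rests on target CR and target PR being separate states, as the table's own columns imply, and, for single-lesion tumors, on absent non-target disease being read as non-target CR.

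How many children would be affected cannot be derived from the documents; the number is probably small. The possible effect on ORSDR is confined to the two circumstances in step 5. The amendment is worth making because it is cheap and the response counts are likely to be small, but the point does not undermine the two-stage design or its decision rule.

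**What to change.** Add a PR column to Table 10: target CR; non-target CR or none present; no new lesion; corticosteroids stable or decreasing; clinical status stable or improved. The result is PR, becoming CR once the CR steroid criterion is met. Put the same rule in the central review charter, since the efficacy endpoints use the central read.

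Separately, reconcile footnote b with footnote a and Section 6.4.1.6 by stating whether newly started physiologic replacement counts as an increase over baseline for PR and SD.

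The cost is a minor amendment to the response table and the charter. No new assessments are needed, because steroid use and clinical status already enter the overall response. The change affects scoring only, not treatment.
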